9.2.5 Solicited Reactogenicity (Expected Reactions)

Assessment of 30-minute Reactogenicity

The 30-minute Reactogenicity is assessed 30 minutes after vaccination on Day 1 and Day 22. The 30-minute Reactogenicity Assessment consists of inspection of the upper arms for presence or absence of redness, swelling, hardness, pain, or tenderness; documentation of the presence or absence of headache, fever, fatigue/malaise, muscle aches, joint aches, nausea, vomiting, and chills.

Appropriate medical treatment must be readily available in case of an anaphylactic reaction following the administration of the study product. Immediate reactions will be assessed by a study physician or appropriately trained medical staff. All reactions that occur during this time will be recorded on the CRF. Any immediate reaction which meets the criteria for an SAE must also be documented on an SAE form.

Emergency medicine will be available at the study clinic in the event there are any adverse reactions or events occurring among subjects participating in this research. If anaphylaxis occurs after vaccination, it

must be treated in accordance with Decision No. 08/1999-TT-BYT, dated 04 May 1999. Treatment for mild reactions after vaccination will be per "Guidance on the treatment of post- injection reactions" of the National Expanded Program on Immunization. The applied treatment methods must be recorded and kept in the subject file.

9.2.6 Solicited Local and Systemic Reactions

Specific local and systemic reactions will be solicited (specifically asked of subjects) while subjects are in the study. These specific reactions, which are signs and symptoms, will be graded by a study clinician using the Toxicity Table for Grading Adverse Events (see Toxicity Table in Appendix B). Grading will use predefined scales based on functional assessment or magnitude of reaction, where available. Where grading scales are not provided, the reaction will be graded for severity based on interference with subject functionally, as for all other AEs (see Section 9.2.1). Severity of redness, swelling, and induration at the injection site should always be graded based on size.

Local Reactions:

- Size of redness (at site of injection) in cm
- Size of swelling (at site of injection) in cm
- Size of induration (hardness at site of injection) in cm
- Pain (at site of injection)
- Tenderness (at site of injection)

Systemic Reactions:

- Fever/body temperature (and body location of measurement)
- Fatigue/malaise
- Generalized muscle aches
- Joint aches/pains
- Chills
- Nausea
- Vomiting
- Headache

Solicited Local and Systemic Reactogenicity will be collected through study Day 7. If a solicited sign or symptom has started during the 7 days post vaccination and continues beyond the 7 days, it will continue to be reported as a reactogenicity symptom. Any solicited sign or symptom starting after 7 days post vaccination will be recorded as an “unsolicited AE”.

9.2.7 Unsolicited Adverse Events

Unsolicited adverse events are any AEs that occur any time after the vaccine/placebo is given (temporally related to study product), whether or not deemed “related” to the product, and are not solicited (specifically asked of the subject). Unsolicited AEs can be observed by study staff while the subject is at a clinic for a study visit or reported by the subject at any time. Any solicited sign or symptom starting after 7 days post vaccination will be recorded as an “unsolicited AE”.

9.2.8 Serious Adverse Events

An SAE is defined as an AE that meets one of the following conditions:

- Death.
- Life-threatening (subject at immediate risk of death). (*This means that the subject was at risk of death at the time of the event; it does not refer to an event that hypothetically might have caused death if it were more severe.*)
- Requires inpatient hospitalization or prolongation of existing hospitalization.
- Results in congenital anomaly/birth defect. (*Only in the case of a woman becoming pregnant during the study period after administration of at least one injection of study product. All pregnancies must be followed to term and outcome reported to IVAC and regulatory agencies.*)
- Results in a persistent or significant disability or incapacity.
- Important medical events that might not result in death, be life-threatening, or require hospitalization might be considered SAEs when, based upon appropriate medical judgment, the event might jeopardize the well-being of the subject and require medical or surgical intervention to prevent one of the outcomes listed above. (*Medical and scientific judgment should be exercised in deciding whether reporting these events is appropriate.*)

All SAEs must be reviewed and evaluated by a study clinician (SAE relationship to study vaccine must be evaluated as outlined in Section 9.2.3) and recorded on an SAE form and reported, as specified in Section 9.3. All such SAEs should also be followed until satisfactory resolution or until the investigator deems the event to be chronic or the patient to be stable.

9.2.9 Procedures for Out-of-Range Laboratory Test Values

Out-of-range laboratory values and AEs:

To the extent possible, all reference ranges for clinical laboratory test results will be pre-specified. The site staff will follow the Toxicity Table for Grading Adverse Events (see Toxicity Table in Appendix B) for grading out-of-range laboratory results. Laboratory values that are out-of-range will not be considered an AE unless they qualify as a Grade 2 or above on the Toxicity Table. It is possible that a laboratory result will be out of the reference range for the laboratory, but not result in a grade on the Toxicity Table. In this case, no grading or reporting as an AE is required. The result will be coded as “ungradable.”

Out-of-range test values may be considered an SAE if two circumstances are met:

1. The value rises to the level of Potentially Life-threatening (Grade 4), and
2. The event is determined by the Principal Investigator to pose an immediate risk of death.

A Grade 4 laboratory result does not, in and of itself, constitute an SAE. Grade 4 places a laboratory value as a potentially life-threatening event, but a Grade 4 laboratory result should not be reported as an SAE unless the PI has determined that it does, in fact, pose an immediate risk of death.

Assessing relatedness and clinical significance of out-of-range laboratory values:

All laboratory results should be reviewed within 36 hours of collection. Investigators should report any laboratory finding Grade 2 and above as an AE. Therefore, the investigator will assess relatedness and clinical significance for these findings.

Clinical judgment always should be used to determine whether a laboratory result requires additional follow up. However, the investigator should redraw any Grade 2 or above laboratory result that is deemed clinically significant at Day 8 at an unscheduled visit to check if the result has normalized.

Any Grade 2 or above laboratory value that is clinically significant and has not returned to normal should be marked by the investigators as “continuing” or “unresolved.” After termination of the trial, the investigator should assure that the subject is referred for appropriate medical follow-up, if indicated.

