8.2 Laboratory Evaluations

8.2.1 Clinical Laboratory Evaluations

All biochemical, immunological, and hematological testing will be performed at labs that have been certified within Vietnam. Some samples may be sent to an additional lab for feedback and assistance to the Vietnam laboratory on testing methods. These outside test results are for technical assistance only and will not be considered in the analysis.

Laboratories will follow written procedures for conducting all laboratory assays.

Laboratory reference ranges will be specified for all tests prior to enrollment of any subject. The reference ranges will be developed based on a survey of ranges from national and regional hospital laboratories. A Toxicity Grading Table will be used to facilitate the grading of the selected out-of-range laboratory parameters (see Appendix B).

A laboratory result that is out-of-range but below Grade 2 does not qualify as an AE to be recorded, and does not require determination of clinical significance or relatedness. A result will be checked as not clinically significant “NCS” if it is outside the lab range but does not rise to a Grade 2 on the AE Table.

Serology for Chronic Viral Hepatitis Infections (PHASE 2 ONLY)

Blood specimens will be evaluated for the following using tests qualified in Vietnam:

- Hepatitis B virus surface antigen (HBsAg)
- HCV antibody using anti-HCV test

Specimen collection will occur on Day S1. Determinant results of a subject’s testing must be obtained from the laboratory prior to administration of any study product.

Pregnancy Test

In order to confirm pregnancy status of females who are able to become pregnant, a qualitative human chorionic gonadotropin (hCG) test will be done on a urine sample.

Pregnancy testing will be done on fertile women on Days S1, S2/D1, and D22. No injection of study product may be given to a fertile woman without a pregnancy test being done or to any woman with a positive pregnancy test.

Clinical Safety Laboratory Tests for Screening and Follow up (PHASE 2 SUBJECTS ONLY)

To monitor potential vaccine toxicity for PHASE 2 SUBJECTS ONLY, blood specimens (fasting not required) will be collected at screening on Day S1, Day 8, Day 22, and Day 29 and evaluated for the following using tests qualified in Vietnam.

- Creatinine
- Alanine aminotransferase (ALT)
- Total bilirubin
- Total protein
- Number of WBC
- Hemoglobin content (Hgb)
- Platelet count

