9.2 Methods and Timing for Assessing and Recording Safety Parameters

9.2.1 Adverse Events

An AE is defined as any untoward medical occurrence in a patient or clinical investigation participant administered a pharmaceutical product, which does not necessarily have a causal relationship with this treatment. An AE can therefore be any unfavorable and unintended sign (including an abnormal laboratory finding), symptom, or disease temporally associated with the use of a medicinal product,

whether or not considered related to the medicinal product. Information to be collected on AEs includes event description, time of onset, clinician's assessment of severity, relationship to study product, and time of resolution/stabilization of the event. AE assessment should be made only by those with the training and authority to make a diagnosis.

In this protocol, laboratory results are considered AEs when the result is Grade 2 or above.

Any medical condition that was present at the time that the subject was enrolled should not be reported as an AE, but should be reported as a pre-existing condition on the Medical History Form. However, if this condition occurs with greater frequency or severity during the study, it should be recorded as an AE.

AEs, including laboratory abnormalities that are Grade 2 and above, should always be assessed for severity and relationship to study products.

This study will collect and record solicited local and systemic reactogenicity and unsolicited AEs. For clarity, solicited reactogenicity refers to AEs specifically asked about during the 7-day post-vaccination period. Unsolicited events are those not specifically solicited, but may be reported by the subject at any time or observed by study staff while the subject is at a clinic for a study visit. If a new solicited event is reported by the subject outside of the 7-day post-vaccination window, this event will be recorded as an "unsolicited AE" because it will be outside of the 7-day window for collection of solicited reactogenicity.

SAEs are defined in Section 9.2.8.

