Comment: The conversion factor used to convert g/dL to mmol/L is 0.6206 and is the most commonly used conversion factor. For grading hemoglobin results obtained by an analytic method with a conversion factor other than 0.6206, the result must be converted to g/dL using the appropriate conversion factor for the particular laboratory.							
Hemoglobin, Low (g/dL; mmol/L) ≥ 13 years of age (male only)	10.0 to 10.9 6.19 to 6.76	9.0 to < 10.0 5.57 to < 6.19	7.0 to < 9.0 4.34 to < 5.57	< 7.0 < 4.34			
≥ 13 years of age (female only)	9.5 to 10.4 5.88 to 6.48	8.5 to < 9.5 5.25 to < 5.88	6.5 to < 8.5 4.03 to < 5.25	< 6.5 < 4.03			
Platelets, Decreased (cells/mm ³ ; cells/L)	100,000 to < 124,999 100,000 x 10⁹ to < 124,999 x 10⁹	50,000 to < 100,000 50,000 x 10⁹ to < 100,000 x 10⁹	25,000 to < 50,000 25,000 x 10⁹ to < 50,000 x 10⁹	< 25,000 < 25,000 x 10⁹			
WBC, Decreased (cells/mm ³ ; cells/L) > 7 days of age	2,000 to 2,499 2,000 x 10⁹ to 2,499 x 10⁹	1,500 to 1,999 1,500 x 10⁹ to 1,999 x 10⁹	1,000 to 1,499 1,000 x 10⁹ to 1,499 x 10⁹	< 1,000 < 1,000 x 10⁹			

LABORATORY				
PARAMETER	GRADE 1 MILD	GRADE 2 MODERATE	GRADE 3 SEVERE	GRADE 4 POTENTIALLY LIFE-THREATENING
CHEMISTRIES		Standard International Units are listed in italics		
ALT or SGPT, High Report only one	1.25 to < 2.5 x ULN	2.5 to < 5.0 x ULN	5.0 to < 10.0 x ULN	≥ 10.0 x ULN
Total Bilirubin, High > 28 days of age	1.1 to < 1.6 x ULN	1.6 to < 2.6 x ULN	2.6 to < 5.0 x ULN	≥ 5.0 x ULN
Creatinine, High	1.1 to 1.3 x ULN	> 1.3 to 1.8 x ULN OR Increase of > 0.3 mg/dL above baseline	> 1.8 to < 3.5 x ULN OR Increase of 1.5 to < 2.0 x above baseline	≥ 3.5 x ULN OR Increase of ≥ 2.0 x above baseline
Total Protein (FDA Table)	5.5 – 6.0	5.0 – 5.4	< 5.0	--

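### Phase 2 monitors white-cell counts but Appendix B grades only low ones, so under 9.2.9 and 8.2.1 an isolated high count is not recorded as an adverse event

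*Protocol*

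**What the plan says.** Protocol 8.2.1 schedules clinical safety bloods at S1 and on Days 8, 22 and 29, and gives the purpose: "To monitor potential vaccine toxicity for PHASE 2 SUBJECTS ONLY". The WBC count is on the list. Appendix B, which supplies the grades, has one white-cell row, "WBC, Decreased".

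Three passages decide when a laboratory result becomes an AE.

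- **9.2.9** is restrictive and names the table: "Laboratory values that are out-of-range will not be considered an AE unless they qualify as a Grade 2 or above on the Toxicity Table". For results outside the reference range that get no grade it adds: "In this case, no grading or reporting as an AE is required". Such results are coded ungradable.
- **8.2.1** says that an out-of-range result below Grade 2 "does not qualify as an AE to be recorded, and does not require determination of clinical significance or relatedness". It has the result marked NCS (not clinically significant) when it is "outside the lab range but does not rise to a Grade 2 on the AE Table".
- **9.2.1** is wider. Its general definition of an AE covers "any unfavorable and unintended sign (including an abnormal laboratory finding"). Its laboratory rule sets the same threshold without naming the table: "In this protocol, laboratory results are considered AEs when the result is Grade 2 or above".

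Section 9.2.2 adds a generic Grade 1 to 4 scale for events that the table does not list.

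**The concern.** A test drawn to look for toxicity has one direction that the grading table does not cover, and the AE rules for laboratory values depend on that table. A high count in a subject who is otherwise well and has no diagnosis would be marked not clinically significant or ungradable, however high it was. Nobody would be required to judge whether the vaccine caused it.

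Laboratory AEs are not solicited events, so they fall in the unsolicited-AE endpoint, as raised ALT and bilirubin did in the Phase 1 results (Protocol 2.1.3, Table 6). That endpoint goes to the DSMB in its review before Phase 3 (Protocol 9.5.2; interim SAP section IX). A reader of the AE tables would see zero events of raised WBC in every arm and could take this as evidence, although the rule fixes the result in advance.

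**Working it through.** There is no formula or plan figure to reproduce. The check sets the passages side by side and follows one case through them.

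**1. Tests drawn against rows available.** Protocol 8.2.1 lists seven tests. Appendix B grades them as follows.

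| Test | Direction graded |
|---|---|
| Hemoglobin | low |
| Platelets | low |
| WBC | low |
| ALT | high |
| Total bilirubin | high |
| Creatinine | high |
| Total protein | low (from the listed cut-offs) |

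No row grades a high WBC.

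**2. The case.** Take a Phase 2 subject whose WBC on Day 8, 22 or 29 is above the laboratory's upper limit of normal (ULN), with no symptoms and no diagnosis.

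- Grade: none, because there is no row.
- AE: no. Section 9.2.9 requires Grade 2 or above on the table.
- Relatedness and significance: 8.2.1 does not require them. The result is marked NCS under 8.2.1 and ungradable under 9.2.9, so even the code differs between the two sections.
- Redraw at an unscheduled visit (9.2.9): the stated rule starts at Grade 2, so it is not triggered.
- Laboratory SAE route (9.2.9): needs Grade 4, so it is not available.

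None of these answers depends on how high the count is.

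**3. Does the 9.2.2 scale change the answer?** It is unclear whether it applies. Section 9.2.2 opens by including laboratory results of Grade 2 and above, which presupposes a grade. Appendix B refers the reader back to the protocol only for clinical AEs that are not in the table. Suppose the scale does apply. Its Grade 1 is an event needing little or no treatment that does not disturb daily activities. An asymptomatic high WBC fits that description and stays at Grade 1, below the Grade 2 threshold in 9.2.1 and 9.2.9. For this case both readings therefore end with no AE.

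**4. How many results the rules govern.** Inputs: 300 Phase 2 subjects, 200 on vaccine and 100 on placebo (Protocol 8.2.2 table), and 3 draws after the first injection (Days 8, 22, 29).

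- All subjects: 300 × 3 = 900 scheduled draws
- Vaccine arms: 200 × 3 = 600
- Placebo: 100 × 3 = 300

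These counts assume full attendance. Phase 3 has no safety bloods and is not affected.

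**The case against.** The strongest reply is that little is lost. Section 9.2.9 has all laboratory results reviewed within 36 hours and leaves follow-up to clinical judgement whatever the grade. Section 9.2.4 records an illness behind the count under its diagnosis. Fever, chills, malaise and local reactions are solicited for seven days after each injection. The interim SAP summarises post-vaccination laboratory data by visit, if available (section VIII), and reports minima and maxima by group (section VI.B), so an extreme count could appear as a group maximum. Appendix B is a table for certain events and grades every parameter in one direction only. The clause on ungraded values also has an ordinary purpose: Appendix B says elsewhere that values between the normal limit and Grade 1 are not graded.

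Most of this stands, and it limits the point to an isolated high count with no diagnosis. It does not remove the point. A maximum shows one value per arm and visit. It does not show how many subjects were high, whether the rise was judged related, or how it resolved. AE listings would not include a value that the rules say is not an AE.

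A reader might infer more than the documents support, in three ways.

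- **That a high WBC can never be reported.** The ungraded-value clause says that AE reporting is not required, which is not a prohibition, and the diagnosis route stays open.
- **That 9.2.2 is disabled for laboratory values.** No sentence says so. The difficulty is that its reach is unclear and that it would generally give Grade 1.
- **That screening has the same hole.** The note in 5.3 waives only minor deviations, and the exclusion criteria leave other abnormalities to the investigator without needing a grade.

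**Conclusion.** The point holds in this form. In Phase 2, sections 9.2.9 and 8.2.1, read with Appendix B, keep an isolated high WBC of any size from being recorded as an AE or assessed for relatedness. They are not reconciled with 9.2.1 and 9.2.2. A zero count of such AEs in the DSMB report would come from the table and would say nothing about the data.

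The size cannot be put as a number of missed events. The 900 scheduled post-vaccination draws are the results that the rules govern, one third of them in placebo subjects. Neither document gives a frequency of raised counts or a cut-off for a high WBC. The conclusion rests on the sections being applied as written and on the subject having no diagnosis that would be recorded instead. The primary immunogenicity endpoint and Phase 3 are untouched. This is a modest gap in safety capture that is cheap to close.

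**What to change.** 1. Reconcile 9.2.9 and 8.2.1 with 9.2.1 and 9.2.2. State whether an out-of-range value in a monitored parameter or direction with no row is graded, and by which scale. Use one code for such results in place of two.
2. Add an increased-WBC row to Appendix B, with cut-offs set by the medical officer. None is proposed here. Do not rely on 9.2.2 alone, since it would leave an asymptomatic value at Grade 1.
3. In the interim report for the DSMB, tabulate the number and percentage of subjects with WBC above the laboratory ULN, by arm and visit. The counts are already collected, and 8.2.1 requires reference ranges to be specified before enrolment.

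The final SAP for the Phase 3 cohort describes Phase 2 in the past tense, so the draws may be complete. If they are, make the tabulation in item 3 from the existing data and state in the report that the AE tables could not show raised WBC.

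The cost is one table row, a short text change, one extra table and, if the rule is changed before the draws, a few more AE forms.

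### Protocol 9.2.9 bars a Grade 4 laboratory result from SAE reporting unless it is an immediate risk of death, which conflicts with the SAE definition in 9.2.8

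*Protocol*

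**What the plan says.** Three parts of Protocol section 9 bear on when a laboratory finding is serious.

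- **When it is an AE.** Section 9.2.1: "In this protocol, laboratory results are considered AEs when the result is Grade 2 or above". Section 9.2.4 repeats this.
- **When an AE is serious.** Section 9.2.8: "An SAE is defined as an AE that meets one of the following conditions". Six conditions follow. Three matter here: "Requires inpatient hospitalization or prolongation of existing hospitalization"; "Results in a persistent or significant disability or incapacity"; and "Important medical events that might not result in death, be life-threatening, or require hospitalization might be considered SAEs", the last by medical judgment. None depends on severity grade, and none excludes laboratory findings.
- **When a laboratory value is serious.** Section 9.2.9: "Out-of-range test values may be considered an SAE if two circumstances are met". The first is "The value rises to the level of Potentially Life-threatening (Grade 4), and" the second is the Principal Investigator's determination of an immediate risk of death. The section accepts that Grade 4 does not by itself make an SAE, then adds that "a Grade 4 laboratory result should not be reported as an SAE unless the PI has determined that it does, in fact, pose" that risk. It does not refer back to 9.2.8.

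Section 9.3.1 requires SAEs other than deaths and immediately life-threatening events to reach the sponsor within 48 hours. It names hospitalisation, disability and other significant events, with no laboratory exception.

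**The concern.** The protocol gives two tests of seriousness for the same event, and they can disagree. Staff with an abnormal result in hand will turn to 9.2.9, because it is the section on out-of-range values, and it gives the narrower test.

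SAEs over Days 1-91 are one of the five safety endpoints (3.2.2, 12.4.2), and the safety sample-size argument in 12.2 rests on seeing rare vaccine-related SAEs. Neither SAP contains a seriousness definition of its own. Each gives the time window and lists what was filed, so the analysis inherits the site's classification. The DSMB's review of the Phase 2 cohort before Phase 3 (9.5.2) would rest on the same classification. An event not filed as an SAE would also miss the 48-hour report and the medical review of SAEs described in 9.3.1.

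**Working it through.** **Step 1: compare the two rules case by case.**

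| Laboratory AE | Under 9.2.8 | Under 9.2.9 |
|---|---|---|
| Grade 4, immediate risk of death | SAE | SAE |
| Grade 4, hospitalised or disabling, no immediate risk of death | SAE | Not to be reported as an SAE |
| Grade 4, important medical event by judgment, no immediate risk of death | May be an SAE | Not to be reported as an SAE |
| Grade 2 or 3, hospitalised or disabling | SAE | Fails the first circumstance; whether that excludes it is not stated |
| Grade 4, no 9.2.8 condition met | Not an SAE | Not an SAE |

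Rows 2 and 3 are the direct conflict. Row 4 is the ambiguity. Rows 1 and 5 agree. Row 5 appears to be the case that 9.2.9 was written for.

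Appendix B gives no Grade 4 for total protein, so a total protein abnormality can never meet both circumstances in 9.2.9, whatever its consequences.

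**Step 2: who is exposed.** Section 8.2.1 schedules safety laboratory tests for Phase 2 subjects only, at screening and on Days 8, 22 and 29. That is 300 subjects, 100 per arm. Phase 3 subjects have no scheduled safety laboratory tests, so a Phase 3 laboratory AE would have to arise from care outside the schedule.

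**Step 3: what one reclassified event does to the reported figure.** No rate is given, so this illustrates sensitivity and does not estimate frequency. The method is the exact (Clopper-Pearson) two-sided 95% interval that the plan uses.

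- For 0 events in n, the upper bound is 1 − 0.025^(1/n).
- For 1 event in n, the upper bound is the p that solves (1 − p)^n + n·p·(1 − p)^(n−1) = 0.025.

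Check against the table in 12.2 (n = 1100): 0 events gives 0.33% and 1 event gives 0.51%. Both match the protocol.

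Applied to one Phase 2 arm (n = 100):

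- 0 events: 1 − 0.025^(0.01) = 3.62%.
- 1 event: 5.45%. At p = 0.0545 the left side is about 0.0037 + 0.0212 = 0.0249.

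**The case against.** The strongest reply is that 9.2.9 only separates two similar labels. Appendix B calls Grade 4 potentially life-threatening, while 9.2.8 reserves life-threatening for a subject at immediate risk of death. On that reading 9.2.9 clarifies one SAE criterion for a laboratory number and leaves the others alone. The intent is plausible, and the statement that Grade 4 is not serious by itself agrees with 9.2.8. But the sentence that follows goes further: it leaves immediate risk of death as the only route for a Grade 4 result. The direct conflict survives.

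Other routes reduce the problem. Section 9.2.4 asks for the diagnosis, if known, in place of component laboratory values, and a hospitalised diagnosis would be filed under 9.2.8. Section 9.3.1 names hospitalisation without a laboratory exception. Both help, but the first works only once a diagnosis exists, and the second applies to events already treated as SAEs.

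A reader might infer more than the documents support:

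- **That every laboratory SAE must be Grade 4 and an immediate risk of death.** The two-circumstance sentence is permissive. Exclusive wording appears only for Grade 4.
- **That such events vanish from the data.** Every Grade 2 or higher result is still recorded as an AE and assessed for severity and relatedness. The risk is misclassification.
- **That the 24-hour report is lost.** It covers deaths and immediately life-threatening events. A Grade 4 result judged an immediate risk of death remains an SAE under 9.2.9, and 9.2.4 sends the event behind any death to the SAE form. Only the 48-hour report is at stake.
- **That laboratory events are the signal to expect in Phase 2.** Phase 1 had no SAEs. Local reactions dominated (80.6% and 75% of the two vaccine groups), against two ALT and three bilirubin rises.

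**Conclusion.** The concern holds in a limited form. For a Grade 4 laboratory AE that meets a 9.2.8 condition without immediate risk of death, the protocol contradicts itself. For Grades 2 and 3 it is unclear. The consequence is possible misclassification as non-serious, with absence from the SAE endpoint and from the 48-hour report.

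The size cannot be estimated because the documents give no rate of such events, and it is probably small. One event in a Phase 2 arm of 100 would move the reported upper bound from 3.6% to about 5.4%. That assumes the arm otherwise has no SAE and that the site follows 9.2.9 over 9.2.8.

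A reader might carry the illustration over to the 1,100 selected-dose recipients in 12.2 (0.33% against 0.51%). That base is not apt. Only about 100 of those recipients would have scheduled safety laboratory tests, and the final SAP plans 500 Phase 3 vaccinees, not 1,000.

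This is an inconsistency in safety-reporting wording. It does not touch any statistical method, and it should be corrected because the contradiction is plain and the repair is cheap.

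**What to change.** Reconcile 9.2.9 with 9.2.8 and 9.3.1. Replace the two-circumstance rule and the Grade 4 sentence with wording to this effect: a laboratory AE is an SAE if it meets any condition in 9.2.8; a Grade 4 value that meets none of those conditions is not an SAE. This keeps the evident purpose of 9.2.9, that a grade alone does not make an event serious, and settles Grades 2 and 3 and total protein at the same time.

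The cost is a sentence or two of protocol text and possibly a few more SAE forms. No sample size, visit or analysis method changes.
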